9.2 Measurement of Treatment Compliance

Dosing compliance for a specified period is defined as the total number of open-label study medications actually taken by a participant during that period divided by the number of open-label study medications that were expected to be taken during the same period multiplied by 100. The total number of capsules actually taken during a specific period will be calculated

Allergan

SAP 3101-302-002 AGN-241689

from the study medication record. Descriptive statistics for open-label study medication dosing compliance together with the compliance categories (< 80%, 80% - 120%, > 120%) will be summarized only for the atogepant arm at each period between 2 consecutive visits, as well as during the whole open-label treatment period of the study for the Safety Population.

Allergan	SAP 3101-302-002 AGN-241689

Allergan

Allergan

Allergan

Allergan	 SAP 3101-302-002 AGN-241689

11 Safety Analyses

The safety analysis will be performed using the Safety Population. The safety parameters will include adverse events (AEs), clinical laboratory, vital sign, electrocardiographic (ECG), and C-SSRS. For clinical laboratory, vital sign, and ECG, the last nonmissing safety assessment before the first dose of treatment will be used as the baseline for all analyses of that safety parameter. Continuous variables will be summarized by number of participants and mean, SD, median, Q1, Q3, minimum, and maximum values. Categorical variables will be summarized by number and percentage of participants.

11.1 Adverse Events

Adverse events will be coded by system organ class and preferred term using the Medical Dictionary for Regulatory Activities (MedDRA), version 21.0 or newer.

An AE will be considered as a treatment-emergent adverse event (TEAE) if the AE began or worsened (increased in severity or became serious) on or after the date of the first dose of open-label study treatment. For participants randomized to the atogepant arm, an AE that occurs more than 30 days after the last dose of open-label study treatment or Visit 16 whichever comes later will not be counted as a TEAE. For participants randomized to the SOC arm, an AE that occurs after Visit 16 will not be counted as a TEAE. Per case report form instructions, a new AE record will be created for any AE that worsens; therefore, for participants randomized to the atogepant arm, TEAEs can be identified as those AEs with recorded onset date on or after the date of the first dose of open-label study treatment within 30 days after the last dose of open-label study treatment or Visit 16 whichever comes later. For participants randomized to the SOC arm with available Visit 16 information, TEAEs can be identified as those AEs with recorded onset date on or after the date of the first dose of open-label study treatment and up to Visit 16; for participants randomized to the SOC arm but missing Visit 16 information, TEAEs are identified as those AEs with recorded onset date on or after the date of the first dose of open-label study treatment. An AE will be considered as a treatment-emergent SAE (TESAE) if it is a TEAE that also meets SAE criteria. TEAEs that started after the date of last dose of study treatment will be considered as newly emergent.

Overall summary of AEs will be provided on a per-participant basis for categories of TEAEs, treatment-related TEAEs, deaths, TESAEs, and TEAEs leading to study discontinuation.

The number and percentage of participants reporting TEAEs in each treatment group will be tabulated by system organ class and preferred term, and further categorized by severity to the study treatment.

The number and percentage of participants reporting treatment-related TEAEs in each treatment group will be tabulated by system organ class and preferred term.

The number and percentage of participants reporting newly emergent TEAEs in the atogepant arm will be tabulated by system organ class and preferred term.

The number and percentage of patients in the Safety Population who have TEAEs leading to premature discontinuation of the study treatment will be summarized by system organ class, preferred term and treatment group.

The incidence of common ($\geq 2\%$ of participants in any treatment group) TEAEs will be summarized by system organ class, preferred term, and treatment group.

The number and percentage of participants who have TESAE in each treatment group will be tabulated by system organ class and preferred term.

In addition, separate tabular displays will be presented for patients who died, participants with SAEs, and participants with TEAEs leading to premature discontinuation.

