## 6.4 Safety Measures

#### 6.4.1 Adverse Events

Adverse events will be collected from the time of consent through the last visit. For all AEs, the investigator must provide an assessment of the severity, causal relationship to the investigational product, start and stop date, and seriousness of the event (eg, SAE), document all actions taken with regard to the study or control intervention, and detail any other treatment measures taken for the AE. For events noted as SAEs, Allergan must be notified immediately to meet their reporting obligations to appropriate regulatory authorities.

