#### 9.1 Definitions

## 9.1.1 Adverse Event

An AE is any untoward medical occurrence in a clinical study participant associated with the use of atogepant or oral SOC migraine prevention medication, whether or not considered

related. An AE can therefore be any unfavorable and unintended sign (including an abnormal laboratory finding), symptom, or disease (new or exacerbated) temporally associated with the use of atogepant or oral SOC migraine prevention medication. In addition, during the screening period, AEs will be assessed regardless of the administration of a pharmaceutical product.

AEs will be reported by the participant (or, when appropriate, by a caregiver, surrogate, or the participant's legally authorized representative).

The investigator and any qualified designees are responsible for detecting, documenting, and recording events that meet the definition of an AE or SAE and remain responsible for following up AEs that are serious, considered related to atogepant or study procedures, or that caused the participant to discontinue atogepant or oral SOC migraine prevention medication or study (see Section 8.8).

All AEs from the signing of the ICF until the safety follow-up visit (Visit 16), or 30 days after the last dose of atogepant (or 30 days after the last study visit for the oral SOC migraine prevention medication arm) if the safety follow-up visit is not done, will be collected at the timepoints specified in the Schedule of Visits and Procedures (Table 1), and as observed or reported spontaneously by study participants.

Investigators are not obligated to actively seek AE information after conclusion of the study participation.

AEs will be assessed, documented, and recorded in the eCRF throughout the study (ie, after informed consent has been obtained). At each visit, the investigator will begin by querying for AEs by asking each participant a general, non-directed question such as "How have you been feeling since the last visit?" Open-ended and non-leading verbal questioning of the participant is the preferred method to inquire about AE occurrences. Care will be taken not to introduce bias when detecting AEs and/or SAEs. All reported AEs will be documented on the appropriate eCRF.

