## 9.3 Procedures for Reporting a Serious Adverse Event

Any SAE occurring during the study period (beginning with informed consent) until the safety follow-up visit (Visit 16) or 30 days after the last dose of atogepant (or 30 days after the last study visit for the SOC arm) if the safety follow-up visit is not done must be immediately reported but no later than 24 hours after learning of an SAE. SAEs must be reported to Allergan as listed on the Allergan Study Contacts Page and recorded on the SAE form. All participants with an SAE must be followed up and the outcomes reported. The investigator must supply Allergan and the IRB/IEC with any additional requested information (eg., autopsy reports and discharge summaries).

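### SAP 11.1 sets no end to the TEAE window for SOC participants missing Visit 16, unlike the atogepant arm and Protocol 9.1.1 and 9.3

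*SAP*

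**What the plan says.** In the available text only SAP 11.1 defines a TEAE. All participants share the same start, the first dose of open-label treatment. The end depends on arm and on Visit 16:

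- Atogepant: "an AE that occurs more than 30 days after the last dose of open-label study treatment or Visit 16 whichever comes later" is not counted.
- SOC with Visit 16: the window closes at that visit.
- SOC without Visit 16: "for participants randomized to the SOC arm but missing Visit 16 information, TEAEs are identified as those AEs with recorded onset date" at or after first dose. The sentence is complete and gives no closing date.

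The protocol covers the same situation in its collection rules. Section 9.1.1 collects "All AEs from the signing of the ICF until the safety follow-up visit (Visit 16), or 30 days after the last dose of atogepant"; the SOC counterpart is "30 days after the last study visit for the oral SOC migraine prevention medication arm". Both 30-day limits apply when the safety follow-up visit is not done. Section 9.3 repeats the limit for serious events: "30 days after the last study visit for the SOC arm".

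SAP Appendix II lists an update of the SOC definition to deal with a missing Visit 16, so the case was considered. SAP section 19 declares no changes from the analyses in the protocol.

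**The concern.** Protocol 3.1 says that the SOC arm is there to provide comparative safety data over 52 weeks. SAP 11.1 tabulates TEAEs, treatment-related TEAEs and treatment-emergent serious events (TESAEs) by arm. For participants without Visit 16, the counting window is closed in one arm and open in the other.

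Records that arrive after the protocol's limit are not a complete or random set. Under Protocol 9.1.1 sites need not actively look for events once participation has ended, so what does arrive is selective and plausibly weighted to serious events. SAP 17.5 and 17.6 then treat a post-dose event with missing severity as severe and one with missing causality as related. A thinly documented late SOC record could therefore enter the tables in the worst category, while the same record for an atogepant leaver would not enter at all.

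**Working it through.** The plan states no figure to reproduce here; the check sets the window ends side by side. Days count from last dose (atogepant) or from the last study visit of the treatment period (SOC). Visit 16 is due 4 weeks later, on day 28 (Protocol 3.1).

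| Case | Protocol 9.1.1 / 9.3 collection ends | SAP 11.1 TEAE window ends | Difference |
|---|---|---|---|
| Atogepant, Visit 16 missed | day 30 | day 30 | 0 days |
| SOC, Visit 16 missed | day 30 | no end written | unbounded |
| Atogepant, Visit 16 on day 28 | day 28 | max(30, 28) = day 30 | 2 days |
| SOC, Visit 16 on day 28 | day 28 | day 28 | 0 days |

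The atogepant phrase can also be read as 30 days after the later of last dose and Visit 16, which would give 28 + 30 = day 58 in the third row. With Visit 16 missed, both readings give day 30. The conflict at issue is therefore confined to the second row.

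**Can a record with onset on day 31 or later exist?** Three routes are documented:

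1. Protocol 9.1.5 follows events to resolution or stabilization and allows eCRF updates until database lock. SAP 11.1 says that a worsening creates a new record, so a late worsening can carry a late onset date.
2. Protocol 9.4 follows pregnancies to term and treats abnormal outcomes as serious events. An outcome can fall well after the last visit.
3. A site may report a serious event it learns of late, although it had no duty to seek it.

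In each case the record is a TEAE (and, if serious, a TESAE) for an SOC participant without Visit 16, and neither for an atogepant participant without Visit 16.

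**Scale.** The documents give no rate of missed Visit 16. Assuming 5%, 10% or 20% of the planned 200 SOC participants:

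- 200 × 0.05 = 10
- 200 × 0.10 = 20
- 200 × 0.20 = 40

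These are the participants with an open window, not the participants miscounted. A participant changes a table row only if a late record exists and no earlier event already puts that person in the row. Each one who does adds 1/200 = 0.5 percentage points to the SOC incidence, if the SOC Safety Population is 200.

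**After the fix.** The second row becomes day 30 with a difference of 0. Both arms then have a 30-day tail, although from different anchors (last dose and last study visit), as the protocol already has it.

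**The case against.** The strongest reply is that the SOC window is open only on paper. Protocol 9.1.1 and 9.3 stop collection 30 days after the last study visit, so the SAP sentence can be taken to mean every event collected under the protocol. Protocol 8.8 also asks that everyone who discontinues attend Visit 15/ET and Visit 16, and Amendment 2 (Protocol 12.6) has Visit 16 done remotely for all participants, so few may miss it. The visible safety analyses are descriptive, with no between-arm test. All of this stands as an argument about size. It does not close the gap: later-dated records can arrive by the routes above, and the SAP excludes them for atogepant but not for SOC.

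A reader might infer more than the documents support:

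- *That there are three competing TEAE definitions.* Protocol 6.4.1, 9.1.1 and 9.3 set collection and reporting periods. Only the SAP classifies events as treatment-emergent, and for atogepant without Visit 16 it agrees with 9.1.1.
- *That Protocol 6.4.1 loses atogepant events after the last dose.* It says "Adverse events will be collected from the time of consent through the last visit", a general sentence that is silent on a missed Visit 16. Sections 9.1.1 and 9.3 supply the specific rule, so no follow-up is lost.
- *That SOC deaths are inflated.* In the overall AE summary deaths are a category of their own, and the separate displays of deaths and of participants with SAEs are not worded as limited to TEAEs. Only tables restricted to TEAEs are exposed.
- *That planned retention gives the size.* The product 0.60 × 0.65 = 0.39 implies 200 × 0.61 = 122 SOC participants not completing 12 months of treatment. That is not a count of participants missing Visit 16: Protocol 3.1 lets SOC participants switch or stop medication and remain in the study, and the Protocol Summary words these rates as atogepant treatment.

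**Conclusion.** The point holds as an asymmetry in one SAP rule. SOC participants without Visit 16 have no end to their TEAE window, whereas their atogepant counterparts and the protocol's own SOC collection rule both stop at 30 days. Any resulting bias can only raise SOC TEAE and TESAE counts relative to atogepant.

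Its size depends on two quantities absent from the documents: how many SOC participants miss Visit 16, and how many of those have a record with onset beyond day 30. The 5% to 20% range is an assumption used only to show how many windows would be open. If sites keep to the 30-day limit, the effect is probably small. It is still worth correcting, because the TEAE tables serve a between-arm safety comparison and the protocol already supplies the missing limit.

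**What to change.** In SAP 11.1, for SOC participants missing Visit 16, count as TEAEs only events with onset from first dose through 30 days after the last study visit, matching Protocol 9.1.1 and 9.3. Put events with later onset, in both arms, in a separate listing so that nothing is hidden.

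The cost is one SAP sentence, one derivation line and one listing. The downside is that a few late SOC events may move from the TEAE tables to the listing. Aligning the wording of Protocol 6.4.1 with 9.1.1 is optional editorial work and would change no analysis.

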## 3 Study Design

#### 3.1 Structure

This is a multicenter, randomized, open-label, 52-week, long-term safety study conducted in the United States and will enroll approximately 700 participants from approximately 115 sites. Participants will be randomized (5:2) to the following treatment groups: atogepant 60 mg QD or oral SOC migraine prevention medication.

All participants randomized to oral SOC migraine prevention medication will be treated with a medication recognized as safe and effective for the prevention of migraine. The selection of this initial migraine preventive medication is based on investigator judgment in consultation with the participant. For participants who do not tolerate this initial preventive medication or for whom the medication is not sufficiently effective (per investigator judgment), the investigator may choose to:

- Prescribe an alternative medication from the medicines recognized as safe and effective for the prevention of migraine (Section 5.6.3), OR
- Prescribe an alternative migraine preventive medication not listed in the medicines recognized as safe and effective for the prevention of migraine (eg, riboflavin, carbamazepine, gabapentin), OR
- Not prescribe an alternative migraine preventive medication.

The purpose of the SOC arm is to collect comparative safety data for 52 weeks. Therefore, a participant who does not tolerate the initially selected migraine prevention medication, or for whom the medication is not sufficiently effective (per investigator judgment), may continue in the study regardless of which alternative option (1, 2, or 3) listed above the investigator selects. In addition, after the initial migraine prevention medication trial, participants who are prescribed an alternative medication (options 1 or 2), but do not tolerate the alternative migraine prevention medication, or for whom this medication is not sufficiently effective, may continue in the study regardless of which alternative option (1, 2, or 3) listed above the investigator selects. Furthermore, participants for whom investigators choose not to prescribe an alternative prevention medication may be prescribed an alternative medication (option 1 or 2) at any time during the study. This may be repeated as needed throughout participation in the study per investigator judgment.

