The study will consist of a 4-week screening and baseline period, a 52-week treatment period, and a safety follow-up period of 4 weeks. *De Novo* Participants and Study CGP-MD-01 Completers will complete all 16 study visits, including the 28-day screening period.

For clarity, note that the participant must not be randomized until Visit 2 when eligibility has been confirmed.

After the randomization visit, the study visits will occur every 4 weeks for the duration of the 52-week treatment period. Participants will return to the clinic for safety assessments at 4, 8, 12, 16, 20, 24, 28, 32, 36, 40, 44, 48, and 52 weeks relative to their randomization visit. A safety follow-up visit will occur 4 weeks after the last dose of atogepant 60 mg QD or after the last study visit for the SOC arm. For details, please see Table 1, Schedule of Visits and Procedures.

The primary objective of the study is to assess the safety and tolerability of long-term atogepant treatment. The planned safety assessments include collection of AEs, clinical

laboratory determinations, ECGs, vital sign measurements, physical examinations, and the C-SSRS.

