## 5.6.1 Participants Randomized to Atogepant

Only participants randomized to atogepant will be provided with atogepant to be taken on an outpatient basis. Atogepant to be used in this trial is listed in (Table 5–1). Participants will take their first dose of atogepant at the clinic at Visit 2.

Participants will be instructed to take their atogepant at approximately the same time each day. Atogepant will be administered orally for 52 weeks, and participants will be followed for 4 weeks following completion or discontinuation of the atogepant.

[figure not shown]
Table 5–1. Study Intervention

Drug/Dose	Study Intervention Frequency	Route of Administration
Atogepant 60 mg	QD	Oral

QD = daily.

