# 5.6.2 Participants Randomized to Oral SOC Migraine Prevention Medication

All participants randomized to oral SOC migraine prevention medication will be treated with a medication recognized as safe and effective for the prevention of migraine. The selection of this initial migraine prevention medication is based on investigator judgment in consultation with the participant.

[figure not shown]

[figure not shown]
At the end of the open-label treatment period, participants do not need to discontinue oral SOC medication. Oral SOC medication may be continued during the safety follow-up period. Alternatively, the investigator may choose to discontinue oral SOC medication.

[figure not shown]

[figure not shown]

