## 8.8 Early Discontinuation of Participants

A premature discontinuation will occur when a participant who signed the ICF and has been randomized ceases participation in the study, regardless of circumstances, before completion of the study. Participants can be prematurely discontinued from the study for one of the following reasons:

- AE
- Lack of efficacy
- Lost to follow-up
- Non-compliance with study intervention (ie, atogepant)
- Pregnancy
- Protocol deviation
- Site terminated by Allergan
- Study terminated by Allergan
- Withdrawal by participant

Participants may voluntarily withdraw from the study at any time.

Notification of early participant discontinuation from the study and the reason for discontinuation will be made to the sponsor and will be clearly documented on the appropriate eCRF. All randomized participants who prematurely discontinue from the study, regardless of cause, should be seen for final study assessments. The final assessments will be defined as completion of the evaluations scheduled for Visit 15/ET and Visit 16 (safety follow-up), 4 weeks post the last dose of atogepant or after the last study visit for oral SOC migraine prevention arm.

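### By-arm TEAE tables in the visible SAP are crude percentages, but the at-risk window closes by last dose for atogepant and by last study visit for SOC; add matched time-at-risk summaries beside them

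*SAP*

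**What the plan says.** **Metric.** SAP 11.1: "The number and percentage of participants reporting TEAEs in each treatment group will be tabulated by system organ class and preferred term". Treatment-related TEAEs, treatment-emergent SAEs and common TEAEs (at least 2% of participants in any arm) are handled the same way. The visible text contains no person-time rate, time-to-first-event estimate or between-arm test.

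**Window.** Under SAP 11.1 an atogepant TEAE counts up to 30 days after last dose or Visit 16, whichever is later. A SOC TEAE counts up to Visit 16. Protocol 3.1 says the visit "will occur 4 weeks after the last dose of atogepant 60 mg QD or after the last study visit for the SOC arm", and SAP 4 puts the SOC visit 4 weeks after the last treatment-period visit. So the atogepant window is anchored on drug stop and the SOC window on study exit.

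**Follow-up after stopping drug.** On atogepant, "participants will be followed for 4 weeks following completion or discontinuation of the atogepant" (Protocol 5.6.1). On SOC, if the medication is not tolerated or not effective enough, one option is "Not prescribe an alternative migraine preventive medication", and the participant "may continue in the study regardless of which alternative option (1, 2, or 3) listed above the investigator selects" (Protocol 3.1). There are exceptions: a liver-test stop without rechallenge (Protocol 9.5), the C-SSRS withdrawal rule (8.9) and pregnancy (4.5.3) all end participation.

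**Purpose.** Protocol 3.1: "The purpose of the SOC arm is to collect comparative safety data for 52 weeks".

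**What is shown alongside.** SAP 7 gives disposition by arm. SAP 9.1 gives treatment duration and participant-years of exposure by arm, with SOC last dose counted up to Visit 16. SAP 11.1 tabulates TEAEs starting after last dose as newly emergent, but only for atogepant.

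**The concern.** With descriptive tables and no test, readers will set the two columns of percentages side by side. A crude percentage depends on how long participants are observed as well as on their risk. If SOC participants stay in the study after stopping drug, while atogepant participants leave 4 weeks after stopping, events that accrue through the year have more time to appear in the SOC column. If SOC participants leave early, the reverse holds. If risk falls once SOC drug is stopped, the extra SOC time dilutes the SOC figure when it is expressed over that time.

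Disposition and exposure tables would reveal unequal follow-up, but they do not adjust the TEAE comparison. Dividing by SAP 9.1 participant-years would not do so either. They omit the roughly 30 days after last atogepant dose in which TEAEs still count, and all off-drug time of SOC participants who stop and stay. For SOC participants still on drug at Visit 16 they do fit, because "Oral SOC medication may be continued during the safety follow-up period" (Protocol 5.6.2) and last dose is followed to that visit.

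**Working it through.** **1. The plan's own figures.** 700 x 5/7 = 500 and 700 x 2/7 = 200, as stated. Completion (Protocol 7.5, SAP 15): 0.60 x 0.65 = 0.39 at 12 months, or 500 x 0.39 = 195 atogepant participants. The Protocol Summary ties this to atogepant treatment. Protocol 7.5 and SAP 15 word it for all participants. It describes completing treatment; no figure for SOC study retention is given.

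**2. One participant under each rule.** Drug stopped on day 84. Atogepant window: 84 + 30 = 114 days. SOC participant who stays off drug to Week 52: 364 + 28 = 392 days. Ratio 392/114 = 3.4. SAP 9.1 exposure is 84 days in both cases.

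**3. Crude percentages with the same true risk.** Assumptions: annual risk 10%, so lambda = -ln(0.9) = 0.105 per year, constant on and off drug. Atogepant drug stop T is piecewise exponential through 0.60 at 0.5 year and 0.39 at 1 year, with window T + 30 days (mean 0.72 year). SOC study exit X is exponential to retention R at 1 year, with window X + 28 days and mean (1 - R)/(-ln R) + 28/365.25. Crude risk = E[1 - exp(-lambda x window)].

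| SOC retention R (assumed) | Mean SOC window, years | SOC crude | Atogepant crude | Ratio, atogepant/SOC |
|---|---|---|---|---|
| 30% | 0.66 | 6.6% | 7.2% | 1.09 |
| 39% | 0.72 | 7.3% | 7.2% | 0.99 |
| 60% | 0.86 | 8.6% | 7.2% | 0.84 |
| 80% | 0.97 | 9.7% | 7.2% | 0.74 |

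If atogepant completion were 60%, its crude figure would be 8.6%, and the ratios at 39%, 60% and 80% would be 1.18, 1.00 and 0.88. With 39% completion, the SOC retention at which the bias vanishes depends on dropout shape: 38-40% for exponential-type loss, 28-30% for linear loss, 59-63% if all loss falls in the first one to three months, and no such point if all loss follows month 6.

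**4. Lower risk off drug.** Further assumptions: R = 80%; SOC drug stopping also follows 60%/65%, independent of study exit and without switching; the hazard is multiplied by f from 30 days after last dose. The common window is first to last dose + 30 days, or end of AE collection if earlier. Differences are atogepant minus SOC, in percentage points, for 500 v 200. The true on-drug difference is zero. RMSE = sqrt(bias^2 + SD^2).

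| f | SOC crude | Crude bias | Crude SD | Crude RMSE | Common-window 1-KM bias | Its SD |
|---|---|---|---|---|---|---|
| 1 | 9.7% | -2.5 | 2.4 | 3.5 | 0.0 | 3.3 |
| 0.5 | 8.2% | -1.0 | 2.3 | 2.5 | +0.1 | 3.3 |
| 0 | 6.6% | +0.6 | 2.1 | 2.2 | 0.0 | 3.3 |

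For example, sqrt(2.5^2 + 2.4^2) = 3.5. About 188 atogepant and 61 SOC participants remain at risk at Week 52 on the common window. Kaplan-Meier on each arm's own TEAE window does not help: at f = 0.5 and f = 0 it gives 10.0% v 8.5% and 10.0% v 6.9%, an apparent atogepant excess caused by off-drug SOC time.

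**5. Early events only.** With a hazard of 2 per year for 28 days and none afterwards, crude and 1-KM are both about 14.2% in each arm. The common-window person-time rate ratio is nevertheless about 0.8 and 0.9 at 60% and 80% SOC retention. A rate alone would mislead here.

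**The case against.** The strongest reply is that no bias has been shown. SOC retention is not stated, and "Participants may voluntarily withdraw from the study at any time" (Protocol 8.8) applies to both arms. At 39% SOC retention the ratio is 0.99, and the sign depends on dropout shape and off-drug risk. This stands. A reader might infer that the tables will make atogepant look safer than it is. The documents do not support that, only that the windows can differ.

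Second, adjustment has a price. In the illustration the common-window Kaplan-Meier difference has a smaller total error than the crude difference in only one scenario of three, and then narrowly (3.3 v 3.5). Its lack of bias is also built in, because drug stopping was simulated as unrelated to event risk. Protocol 3.1 ties SOC changes to intolerance or lack of effect, so censoring at last dose may be informative. This stands too. It rules out the tempting step of making an on-drug window the main comparison, which would also set aside the off-drug follow-up the protocol deliberately collects.

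Third, the objective and hypothesis concern atogepant alone, and no test is planned. True, but the protocol gives the SOC arm a comparative purpose.

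Fourth, a reader might take the SOC window as unlimited when Visit 16 is missing, since SAP 11.1 states no end. Protocol 9.1.1 already stops collection 30 days after the last SOC study visit, so this is clerical.

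Finally, redacted SAP pages or the separate table specifications may already hold adjusted summaries. That cannot be excluded.

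**Conclusion.** The point holds for the visible text. Crude TEAE percentages are tabulated by arm over windows anchored on different events, and SAP 9.1 participant-years cannot serve as the denominator. Direction and size are unknown in advance. With equal 10% annual risk and 39% atogepant completion, the artefact runs from +0.6 points (7.2% v 6.6%) at 30% SOC retention, through almost nothing at 39%, to -2.5 points (7.2% v 9.7%) at 80%. If risk vanishes off SOC drug, it is +0.6 points even at 80%. These figures rest on assumed SOC retention, event risk and dropout shape. Events confined to the first weeks are essentially unaffected. The uncertainty about direction is itself a reason to fix the rule before the data are compared. This is a worthwhile, inexpensive improvement; it does not invalidate the planned tables.

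**What to change.** Keep crude n (%) in SAP 11.1 as planned, and add:

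1. Mean and total TEAE time at risk by arm.
2. For any TEAE, treatment-related TEAEs and treatment-emergent SAEs, by arm: participants with a first event per 100 participant-years at risk, and Week-52 cumulative incidence (1 minus Kaplan-Meier) with number at risk, both with 95% CIs. Use one window rule in both arms: first dose to last dose of atogepant, or of any SOC-arm preventive (initial or alternative), plus 30 days, or end of AE collection if earlier. Label these as supportive, state that the denominator is this time at risk and not SAP 9.1 participant-years, and print the rate only beside the cumulative incidence.
3. A SOC column in the newly emergent TEAE table, so that events starting after last dose are visible in both arms.
4. A rule in SAP 17.4 for a missing last-dose date in SOC participants who stopped drug. The visible SOC rule covers only treatment still ongoing at end of study.

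As a clerical matter, SAP 11.1 can cite the Protocol 9.1.1 limit for a missing SOC Visit 16.

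**Cost.** SAP wording and a few tables. Most dates are already needed for SAP 9.1, though SOC stop dates may be less complete because the sponsor does not supply that medication. The added estimates are less precise than crude (SD about 3.3 v 2.1-2.4 points in the illustration). They assume uninformative censoring at drug stop, and first-to-last-dose time still counts gaps between SOC medications.
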